All participants will give written informed consent according to institutional guidelines prior to any testing. The Principal Investigators or their designee will obtain consent using a written consent form approved by the Institutional Review Boards of the University of Michigan Medical School (IRBMED). It will contain detailed information regarding the purpose, risks and benefits of participating. Copies of the signed consent form will be given to the subjects; the original consent will remain with the study team.

Compensation

Participants will be compensated \$100 for completing the one-time visit. Participants who have shaved or no hair, or those willing to shave the right side of their temple will be compensated an additional \$75. Participants who are willing to shave an area around their right side of their temple should do this prior to arriving to their scheduled study visit.

Inclusion and Exclusion Criteria

Volunteers are screened using a medical history and demographics questionnaire.

Inclusion Criteria:

- Healthy adults ages 18 – 40.
- Must be right-handed.
- Must have normal or corrected-to-normal vision (while wearing contact lenses).
- Must not be on any medications for any neurological, psychological, or psychiatric conditions.
- Must be English speaking.
- Must be capable of giving written informed consent.

Exclusion Criteria:

- Vision that is not 20/20, or vision that is not corrected to 20/20 while wearing contact lenses.
- History of significant head injury with loss of consciousness.
- Learning disability or other developmental disorder.
- Any impairment (sensory or motor loss), activity, or situation that in the judgment of the study coordinator or Principal Investigators would prevent satisfactory completion of the study protocol.

Methods and Procedures

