We will utilize the BrainSonix BXPulsar 1002 LIFUP System (BrainSonix Inc. <http://www.brainsonix.com/>). FDA has determined that our proposed clinical investigation is a nonsignificant risk (NSR) device study because it does not meet the definition of a significant risk (SR) device under 21 CFR 812.3(m) of the investigational device exemptions (IDE) regulation (21 CFR 812). An IDE application is not required to be submitted to, or approved by, FDA for a NSR study. This device contains a single-element, air-backed, spherical section ultrasound transducer with 61 mm diameter and 80 mm focal depth. The transducer is mounted in a plastic housing filled with deionized, de-gassed water and sealed with a thin polyethylene membrane permeable to ultrasound. The transducer will be coupled to the scalp of the participant using a 3D-printed transducer holder that allows for sonication to occur in conjunction with ultrasonic standoff pads and ultrasound gel. The LIFUP system operates at a fundamental frequency of 650 kHz. Following previous work, we plan to administer a pulse repetition frequency of 10 Hz, pulse width of 0.5 ms, and a duty cycle of 70% to induce an excitatory effect and a duty cycle of 5% to induce a suppressive effect. For each thalamic area, a total of 10 sonifications (in 10 minutes) will be administered, with a derated spatial-peak temporal-average intensity (Ispta) of 720 mW/cm², each lasting 30 s, separated by 30 s pause intervals (**Figure 4**). We will utilize the Brainsight Navigation system, developed by Brainbox Ltd, to ensure precise targeting and positioning of the transducer. At the target location, the estimated peak pressure will be 0.71 MPa, and the ultrasound beam width will be 5 mm. The estimated targeting accuracy (uncertainty) at the desired location is ± 2.5 mm. Electromyography (EMG) recordings will complement the behavioral data, providing valuable information about muscle activity and response patterns during the

study.

[figure not shown]

Figure 4. Conceptual illustration of LIFUP setting and parameter configuration (adapted from ³³ and <https://brainsonix.com/technology/>).

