Experimental Design. The experimental will consist of a 10-minute baseline period (LIFUP-OFF) followed by four 10-minute sessions of stimulating (LIFUP-ON) four thalamic areas. The order of thalamic area stimulation will be counterbalanced across participants and will include the ventral anterior (VA), dorsal anterior (DA), ventral posterior (VP), and dorsal posterior (DP) sections of the thalamus. The center coordinates of these thalamic regions will be derived from a previous study on thalamic parcellation ⁴⁰. Given that previous studies have not indicated any functional lateralization of the thalamic areas, we will target only the left hemisphere for the sake of convenience in this study.

Perceptual Task. The quality of conscious perception will be assessed by a well-established psychometric approach, the near-threshold perceptual task ^{41,42}. This task allows one to compare the neural activity evoked by identical weak stimuli that are sometimes perceived and sometimes remain subliminal (**Figure 5**). It thus rules out potential confounds of variability derived from the differences in physical property of the stimuli. All stimuli will be programmed using E-Prime (Psychology Software Tools, Pittsburgh, PA) and delivered via a laptop computer. Stimuli will be presented at the threshold of subjective recognition. An adaptive thresholding procedure will be conducted whereby image contrast will be titrated to reach a 50% subjective recognition rate for each subject. Stimuli will include two common visual object categories: faces and houses. Participants' task is to report the category ("F" or "H") of an image presented and their recognition experience ("Yes" or "No"). Specifically, they will be instructed to report the object category regardless of their recognition experience and, in cases of unrecognized images, to make a genuine guess (two-alternative choice discrimination). Then, they will be instructed to report whether they see an object, such that even if the object appears unclear or noisy, they should respond "yes", but if they see nothing or only low-level features, they should respond "no".

[figure not shown]

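### Does targeting the left thalamus while asking participants to shave the right temple reveal an error in the plan?

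*Combined protocol and SAP*

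**What the plan says.** Experimental Design names four thalamic sections (VA, DA, VP, DP). It gives the absence of known functional lateralization as the reason for treating one side only: "we will target only the left hemisphere for the sake of convenience in this study". The targets are then fixed by coordinates: "The center coordinates of these thalamic regions will be derived from a previous study on thalamic parcellation".

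The Compensation section speaks of the other side, twice. On payment: "those willing to shave the right side of their temple will be compensated an additional" 75 dollars, the same sum that goes to people with shaved or no hair. On preparation: "Participants who are willing to shave an area around their right side of their temple should do this prior to arriving" for the visit.

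LIFUP Method describes the hardware. "The transducer will be coupled to the scalp of the participant using a 3D-printed transducer holder", with standoff pads and gel. The device is a "spherical section ultrasound transducer with 61 mm diameter and 80 mm focal depth", and a navigation system is used "to ensure precise targeting and positioning of the transducer". No side of the head and no skull site is named there. Figure 4, which illustrates the setting, is not reproduced in the text available; its caption calls it conceptual and adapted from other sources.

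**The concern.** A reader who meets a left target and a right-sided shave, with no sentence connecting them, may suspect that one of the two words is wrong. Three readings are open: the beam enters on the right and crosses to the left thalamus; it enters on the left and the hair preparation is on the unused side; or the target side itself is misstated.

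Participants shave at home, so a wrong instruction could not be put right before the visit. Someone repeating the study could not tell from the methods text whether the approach is from the same side or the opposite side. The inference rests on separating four small targets with a 5 mm beam and a stated accuracy of ± 2.5 mm, so the approach path looks like something that ought to be written down.

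**Working it through.** **Are the statements in conflict?**

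| Section | What it fixes | Side |
|---|---|---|
| Experimental Design | Target in the brain | Left |
| Compensation (payment) | Scalp to be shaved | Right |
| Compensation (preparation) | Scalp to be shaved | Right |
| LIFUP Method | Transducer on the scalp | None given |

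The first row concerns a different object from the second and third, so left and right do not exclude each other. The only device described for which a cleared temple has an evident purpose is the transducer with its gel and pads. EMG is also mentioned, but without a site. Read together, the sections therefore suggest entry at the right temple, although none says so.

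**Does the 80 mm focal depth settle the side?** The documents give no head dimensions, so the following are assumptions: temple to midline 65–80 mm, target 5–20 mm left of midline, a straight lateral path, and focal depth measured from the scalp when no standoff is used.

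- Right entry: half-width plus offset, 65 + 5 = 70 mm to 80 + 20 = 100 mm. Against 80 mm, this runs from 80 − 70 = 10 mm of standoff to a target 100 − 80 = 20 mm beyond the focus.
- Left entry: half-width minus offset, 65 − 20 = 45 mm to 80 − 5 = 75 mm. Against 80 mm, this needs 80 − 75 = 5 mm to 80 − 45 = 35 mm of standoff.

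Standoff pads are planned but their thickness is not given, so both sides include workable paths. The stated depth neither identifies the entry side nor shows an error. Nothing in the conclusion rests on this check.

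**What could it cost?** With 60 participants and 75 dollars each, the payment at stake is at most 60 × 75 = 4,500 dollars. Reaching that needs left entry and all 60 participants to have shaved only the right temple. The lower bound is 0, which is the value under right entry.

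**Does any analysis quantity depend on it?** The endpoints are d' = Z(HR) − Z(FAR) and c = −0.5 × (Z(HR) + Z(FAR)), computed per 10-minute session from yes/no reports. The ANOVA compares the baseline with four sessions labelled by thalamic section. Entry side appears in none of these. On the unfavourable reading, a participant who shaved the unused temple is coupled as any unshaven participant would be, and the plan already admits unshaven participants.

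**The case for a change.** The best case for asking for a change is that the remedy is one sentence, that a slip cannot be excluded, and that the shaving instruction is acted on before anyone at the site can correct it. Navigation to coordinates tells the operator where the focus belongs. It does not tell a participant at home which temple to prepare, or a later reader which way the beam travelled. The most serious variant is a slip in the target side itself, since it would then be unclear which thalamus is sonicated.

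Part of this stands. The available text never gives target side, entry side and hair-preparation side together, and a published methods section would be clearer if it did. The rest is weak. The right side is named in two consecutive sentences. The left side comes with its own stated reason. No text points to a mistake in either place. The protocol's hypotheses are framed by thalamic section, not by hemisphere, and its premise is that no lateralization has been shown. Even the most serious variant would therefore leave the planned comparisons as they are. What the figure and the consent pages show is unknown, and their absence here cannot be counted against the plan.

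**Conclusion.** The observation about the text is correct: no visible sentence links the entry side to the target side. It does not amount to a contradiction, because the two sides refer to different things and fit together under a right-sided approach to a left-sided target. Confidence is high for the textual observation only; no error has been shown, and this review does not say which side is right.

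Following the plan as written leaves the results interpretable. The target is set by navigation, shaving is voluntary, and endpoints, sample size, significance threshold and ANOVA are untouched. The only quantity that could move is the extra hair payment, with a ceiling of 4,500 dollars and no evidence that it differs from zero. The conclusion assumes that the shaving serves transducer coupling and that the operators know the entry side when they position the device. This is a gap that those running the study fill sensibly, and no change to the plan is needed.

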Figure 5. Visual task design. During each 10-min session, participants will complete an image recognition task. Stimuli (faces, houses, and scrambled images) will be presented at the threshold of subjective recognition. Participants' task is to report the category ("F" or "H") of the image presented and their recognition experience ("Yes" or "No").

The stimulus set will include real and scrambled images, the latter will be created by phase-shuffling of a randomly chosen real image from each category to preserve category specific low-level image features^{41,42}. Because scrambled images serve as "catch trials" to determine the subjects' baseline tendency to give positive responses to a question about their recognition experience. The pre-stimulus interval will vary randomly from trial to trial between 2 and 4 seconds to prevent stimulus timing predictability. The stimuli will be presented in a randomized order to prevent category predictability.

Primary Outcome Measure

Perceptual criterion (c) and sensitivity (d') derived from the Signal Detection Theory (SDT) analysis. These measures will be assessed over a timeframe spanning from the baseline to 60 minutes after the LIFUP stimulation.

Data Analysis and Statistics

For each 10-min session, we will calculate sensitivity (d') and criterion (c) using subjective reports of recognition as "yes" or "no". (d') indicates the ability to discriminate between real and scrambled images. It is computed by subtracting the z-transformed False Alarms Rate (FAR) from the z-transformed Hit Rate (HR): $d' = Z(HR) - Z(FAR)$, where Z is an inverse normal cumulative distribution function. (c) reflects the tendency to make "yes" reports to indicate recognition, regardless of whether the stimulus is a real or a scrambled image, which is computed as: $c = -0.5 \times (Z(HR) + Z(FAR))$. We will also calculate percent of correct responses as an operational measure of two alternative-forced-choice sensitivity using subjective category reports, i.e., responses to the first question: "Face" or "House".

We will conduct a repeated-measures ANOVA, considering measurements taken during both the baseline and the four thalamic areas' stimulation sessions. This analysis will be

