performed at the group level to assess the effects of LIFUP on the perceptual measures. To determine statistical significance, we will apply a false discovery rate (FDR) correction and set the threshold at $\alpha < 0.05$. This approach will help us identify any significant differences between the baseline and the different thalamic area stimulations in terms of sensitivity (d') and criterion (c).

Anticipated Results and Interpretation

We expect to observe differential changes in the perceptual outcomes based on the LIFUP stimulation of different thalamic areas. We anticipate that stimulation of the ventral anterior thalamus will decrease criterion (c), indicating a shift of the decision criterion in the liberal direction. During exciting the dorsal posterior thalamus, we expect an increase in sensitivity (d'), reflecting a higher sensitivity in differentiating between stimuli. Conversely, when inhibiting the ventral anterior thalamus and the dorsal posterior thalamus, we expect the opposite effects on criterion (c) and sensitivity (d') compared to the outcomes seen during their respective excitations. The effects of stimulating the dorsal anterior thalamus and the ventral posterior thalamus are expected to lie between the effects of ventral anterior and dorsal posterior thalamic stimulation. These findings should provide valuable insights into the specific contributions of these thalamic regions in shaping conscious experiences.

Power Analysis

We considered a recent review article that summarized 25 LIFUP studies in humans. These studies had sample sizes ranging from 1 to 50, with a median value of 16. Since the neuromodulation effect is dependent on various factors, such as parameter settings and specific brain regions targeted, determining a prior effect size is challenging. However, we have planned a subject number of 30 per group, which exceeds the median sample size reported in the literature. With a larger sample size, we aim to enhance the statistical power, reliability and sensitivity of our findings, enabling us to draw robust conclusions about the neuromodulatory effects of LIFUP on conscious perception.

Biological Variables

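### The 60-minute outcome window does not match the described sessions, and the only comparisons named, each area against a baseline that always comes first, cannot separate area effects from carry-over or time on task

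*Combined protocol and SAP*

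**What the plan says.** **Window.** The Primary Outcome Measure section defines c and d' and adds: "These measures will be assessed over a timeframe spanning from the baseline to 60 minutes after the LIFUP stimulation".

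**Schedule.** Experimental Design gives a 10-minute LIFUP-OFF baseline "followed by four 10-minute sessions of stimulating (LIFUP-ON) four thalamic areas". Recruitment and Compensation describe a single visit. The legend of Figure 5 places the task within each 10-minute session.

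**Order.** "The order of thalamic area stimulation will be counterbalanced across participants". The scheme is not named, and baseline comes first for everyone. No gap or washout between sessions is described.

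**Analysis.** Data Analysis and Statistics says "For each 10-min session, we will calculate sensitivity" and criterion. It then plans a repeated-measures ANOVA "considering measurements taken during both the baseline and the four thalamic" areas' stimulation sessions. With FDR correction, the aim is to "identify any significant differences between the baseline and the different thalamic area stimulations". No contrast between areas is named, and no term for session position or preceding area is described.

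**Prediction.** Anticipated Results and Interpretation expects ventral anterior (VA) stimulation to act on c and dorsal posterior (DP) stimulation to act on d'. The effects of the dorsal anterior (DA) and ventral posterior (VP) areas "are expected to lie between the effects of ventral anterior and dorsal posterior thalamic stimulation".

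**The concern.** Two things do not fit together.

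First, the primary outcome carries a time frame that the described sessions do not supply. If a follow-up hour is intended, it is neither scheduled nor analysed. If it is not intended, the outcome definition is wrong as written.

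Second, the scientific claim is that areas differ from one another, but the stated tests ask only whether each area differs from baseline. In a single visit with a fixed first baseline, whatever accumulates over the visit sits in all four of those differences. An area with no effect of its own could then be reported as having one. The plan predicts graded effects across areas, so small shifts in areas that do nothing could be taken as support for that gradient.

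**Working it through.** **1. Session length reproduces.** LIFUP Method gives 10 sonications of 30 s separated by 30 s pauses: 10 x (30 + 30) = 600 s = 10 min, as stated.

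**2. The window does not.** Session time is 10 + 4 x 10 = 50 min. The last measurement ends:
- 40 min after the first stimulation starts;
- 30 min after the first area's session ends;
- 0 min after the last stimulation ends.

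None of these is 60. Counted from the first sonication, the sessions would fill the window only with (60 - 40)/3 = 6.7 min in each of the three gaps. Repositioning makes some gap plausible, since navigation is used "to ensure precise targeting and positioning of the transducer", but no gap is stated.

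**3. Carry-over against baseline.** Let an area's effect carry into the next session only. Each area follows another area in three of four positions; baseline never does. If order is balanced for preceding area (all 24 orders, or a four-sequence Williams square), each other area precedes a given area in one quarter of participants:

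bias (area minus baseline) = (sum of the other three areas' carry-overs)/4.

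With equal carry-over K this is 0.75K. If carry-over persists undiminished it is 1.5K.

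**4. Time on task.** The four stimulation sessions lie 1, 2, 3 and 4 steps after baseline. With a linear practice or fatigue drift g per session, every area-minus-baseline difference gains g x (1 + 2 + 3 + 4)/4 = 2.5g. Counterbalancing makes this equal across areas, so it cancels between areas. It does not cancel against baseline.

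**5. Area-versus-area contrasts.** Equal carry-over also cancels. Unequal carry-over does not. If only VA has an effect tau and carries over a fraction L of it, each inert area shifts by L x tau/4 (one session) or L x tau/2 (persistent). At L = 1 the VA-DP contrast becomes 0.75 tau or 0.50 tau.

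**6. Illustration.** The documents give no effect size or carry-over size, so all of the following are assumptions: only VA active; tau 0.5 or 0.8 SD of the area-minus-baseline difference; L from 0.5 to 1; n = 30 in Williams sequences of 8/8/7/7; independent session errors; two-sided paired t-tests; Benjamini-Hochberg at 0.05; 20,000 simulated trials per case. The table gives the chance that an inert DA or VP is declared different from baseline. The eight-test family adds four null d' tests.

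| Carry-over | Four tests, tau 0.5 | Four tests, tau 0.8 | Eight tests, tau 0.5 | Eight tests, tau 0.8 |
|---|---|---|---|---|
| None | 2% | 3% | 1% | 1% |
| One session | 3-6% | 5-12% | 2-3% | 3-7% |
| Persistent | 6-18% | 13-44% | 4-11% | 8-32% |

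In the one-session and persistent cases the unadjusted DA-DP test rejects in about 2.5-5% of trials, so it is not inflated. Unadjusted power for VA-DP at tau 0.5 and L = 1 falls from 75% to just under 50% (one session) or 22-25% (persistent).

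**7. What a sensitivity model recovers.** The model uses the four stimulation sessions, with participant, position, area and preceding area. At L = 1 and equal sequence sizes the VA-DP estimate moves from 0.75 to 1.00 tau (one session), 0.63 to 0.84 tau (halving each session) and 0.50 to 0.63 tau (persistent). The variance ratio is 0.06875/0.0625 = 1.10.

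**The case against.** Several stronger readings are tempting, and the documents do not support them.

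- *A reader might infer that it is unclear what enters the primary analysis.* It is not. Data Analysis and Statistics fixes one value of c and d' per 10-minute session and lists the five sessions in the ANOVA. The window can also be read as a loose outer bound, and then no analysed number changes.
- *A reader might infer from the 60-minute window that effects outlast a session.* The window allows for that but does not establish it, and nothing else in the documents does.
- *A reader might infer that carry-over always shrinks contrasts between areas.* It does so only when areas carry over unequally, as in the VA-only illustration.
- *A reader might infer that the planned tests could not expose a false gradient.* In the illustration an inert DP shifts about as much as DA and VP, so DA and VP do not truly lie between VA and DP. DP is compared with baseline, so its estimate gives a partial warning. At tau 0.8, L = 1 and persistent carry-over, DP is flagged in about 49-50% of trials and DA and VP in about 44%.

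It is also fair that the largest rates need a strong effect, full carry-over without decay and a four-test family. Both c and d' are tested, so eight tests is a natural family, and its rates are lower. Carry-overs of opposite sign could partly cancel.

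What stands is structural. Baseline is always first, it is the only named comparator, and no ordering of the four areas changes that.

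**Conclusion.** The point holds in two parts.

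The outcome window and the session schedule disagree and must be reconciled. This affects the definition of the primary outcome, not the identity of the values in the ANOVA.

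The named comparisons do not test the claim that areas have distinct roles. Any carry-over, practice or fatigue stays in every area-versus-baseline difference whatever the counterbalancing. That follows from the design. Its size does not, because the documents give no carry-over figure. The illustrated 3-12% and 6-44%, against 2-3%, are conditional on only VA being active and on the stated ranges. Area-versus-area contrasts remove time on task and equal carry-over. They are the direct test of the study's aim and use data already collected, so adding them is worthwhile even if carry-over proves negligible.

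**What to change.** 1. **Reconcile Experimental Design with Primary Outcome Measure.** Either end the window at the close of the fourth stimulation session, or state the event from which the 60 minutes is counted, when post-stimulation tasks take place, and whether they enter the ANOVA or a separate analysis.
2. **Keep the planned ANOVA as primary and name area-versus-area contrasts** as the basis for any claim that areas differ. For c: VA-DP, DA-DP, VP-DP. For d': DP-VA, DA-VA, VP-VA. Apply FDR correction to these six as their own family within each arm.
3. **Add a sensitivity model for these contrasts** on the four stimulation sessions, with session position and preceding area. Name an order scheme balanced for preceding area. A Williams square is one option; 30 is not a multiple of 4, so it would run 8/8/7/7 per arm.
4. **State the limitation** that area-versus-baseline differences may include carry-over and time-on-task effects, and that the sensitivity model does not correct them.

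A comparison restricted to each participant's first stimulated area should be omitted or be descriptive only. It has 7-8 participants per area per arm, with 43-50% power at 0.8 SD.

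**Cost.** Some wording, a sequence list, six more tests per arm and one extra model, with no added participants. The sensitivity model costs about 10% more variance for VA-DP. It removes one-session carry-over but only part of longer carry-over. Visit time grows only if post-stimulation tasks were already intended.

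### The face/house response is summarised only as raw percent correct, which a lean toward one category lowers; a face/house d' on real images should be added as a named secondary outcome

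*Combined protocol and SAP*

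**What the plan says.** Under Perceptual Task, each trial presents a single image and asks two questions: its category (F or H), then whether an object was recognised (yes or no). On the first, "they will be instructed to report the object category regardless of their recognition experience"; a participant who did not recognise the image is told to guess. Difficulty is set so that "image contrast will be titrated to reach a 50% subjective recognition rate for each subject".

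Under Data Analysis and Statistics, d' and c are computed from the yes/no answers, with real images as signal and scrambled images as noise. This d' "indicates the ability to discriminate between real and scrambled images". The category answers get one sentence: "We will also calculate percent of correct responses as an operational measure of two alternative-forced-choice sensitivity using subjective category reports". No face/house d' or face/house bias is planned.

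The Primary Outcome Measure section lists only c and d'. The repeated-measures ANOVA is described as covering the perceptual measures, without listing them. The aim of the significance testing is then to "identify any significant differences between the baseline and the different thalamic area stimulations in terms of sensitivity (d') and criterion (c". Percent correct has no stated hypothesis, no stated place in the FDR correction and no stated role in interpretation.

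**The concern.** The plan labels the score a two-alternative forced-choice sensitivity. In a task where two stimuli are compared on each trial, percent correct is often taken as a reasonable stand-in for sensitivity. Here one image is classified, so the score mixes discrimination with any preference for answering face or house. Contrast is titrated to 50% recognition, so about half of real-image trials are expected to be unrecognised and answered by guessing, and a preferred guess enters most easily there.

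Two gaps add to this. The sentence takes responses to the first question without restricting them to real images, although a category answer is also given to scrambled images. And it is unclear whether the measure is tested at all.

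At stake is the usefulness of the second discrimination measure that the trial collects. The study aims to separate an effect on c from an effect on d'. A bias-free category measure would help interpret a yes/no d' effect. As specified, the measure is bias-dependent and has no defined use.

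**Working it through.** The plan states no figure on this point, so there is none to reproduce. The one-image format and the percent-correct score come from the plan. Face/house d' and bias c are assumptions, because the documents give neither, and so are equal variance and an equal number of faces and houses.

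**1. Percent correct as a function of bias.** Let c > 0 mean a lean toward answering house. Then P(F | face) = Φ(d'/2 − c), P(H | house) = Φ(d'/2 + c), and

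PC = 0.5 × [Φ(d'/2 − c) + Φ(d'/2 + c)].

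For d' = 1:
- c = 0: 0.5 × (0.6915 + 0.6915) = 69.1%
- c = 0.25: 0.5 × (0.5987 + 0.7734) = 68.6%
- c = 0.5: 0.5 × (0.5000 + 0.8413) = 67.1%
- c = 1: 0.5 × (0.3085 + 0.9332) = 62.1%

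**2. Range over assumed d'.**

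| d' | c = 0 | c = 0.25 | c = 0.5 | c = 1 |
|---|---|---|---|---|
| 0.5 | 59.9% | 59.6% | 58.7% | 56.1% |
| 1.0 | 69.1% | 68.6% | 67.1% | 62.1% |
| 1.5 | 77.3% | 76.6% | 74.7% | 68.1% |
| 2.0 | 84.1% | 83.4% | 81.2% | 73.9% |

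Bias alone costs 0.3 to 0.7 points at c = 0.25, 1.1 to 2.9 at c = 0.5 and 3.8 to 10.3 at c = 1.

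**3. What this does to an inferred sensitivity.** Ignoring bias, d' = 2 × Z(PC). A true d' of 1 then reads as 2 × Z(0.6707) = 0.88 at c = 0.5 and 2 × Z(0.6209) = 0.62 at c = 1. By contrast, Z(P(F | face)) − Z(P(F | house)) = (d'/2 − c) − (−d'/2 − c) = d' at every c.

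**4. Stable versus changing lean.** If the lean is the same in every session, a rise in d' from 1.0 to 1.5 shows as 77.3 − 69.1 = 8.2 points at c = 0, 74.7 − 67.1 = 7.6 at c = 0.5 and 68.1 − 62.1 = 6.0 at c = 1. The effect is compressed but not invented. A false change needs the lean itself to differ between sessions.

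**5. The label.** With two stimuli compared per trial, unbiased d' = 1 gives Φ(1/√2) = 76.0%, against 69.1% here. Converting 69.1% as if it came from such a task returns √2 × Z(0.6915) = 0.71. The plan does not propose this conversion, but its label invites it.

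**6. Scrambled trials.** Their share is not given. If they were scored and answered at chance, an assumed share of 20% turns 69.1% into 0.8 × 0.6915 + 0.2 × 0.5 = 65.3%. A share of one third gives (2/3) × 0.6915 + (1/3) × 0.5 = 62.8%. Chance responding is itself an assumption, since the scrambling is meant to keep category-specific low-level features.

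**The case against.** The strongest reply is that this is a minor descriptive measure and that little follows from its weakness. Much of that stands.

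- **Different biases.** A reader might infer that the expected ventral anterior effect would contaminate percent correct. The documents do not support this. The bias expected to move is the tendency to answer yes to the recognition question. A face/house lean is another axis, and nothing in the plan predicts that stimulation will change it.
- **The primary d'.** A reader might infer that the primary d' is mere self-report, and could rise only because people say yes less often to scrambled images. It is scored against known real or scrambled status. If false alarms fall while hits hold, real/scrambled discrimination has improved. If yes answers fall on both image types, that is a change in c, and d' is unaffected under equal variance.
- **No checking role.** The plan never presents percent correct as an objective check on d', so it cannot be faulted for failing as one.
- **Tested or not.** It would be too strong to say that percent correct is untested. The general reference to perceptual measures could include it; it is only not named in the closing sentence.
- **Size.** At d' = 1 and c = 1 the participant answers house on about 81% of real-image trials (1 − (0.3085 + 0.0668)/2). That is an extreme lean, and a stable one largely cancels between sessions.

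What remains is that the score is bias-dependent, its trial set is undefined and its inferential status is unclear, while a bias-free alternative is available from the same responses.

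**Conclusion.** The point holds as a limited one. Percent correct in this one-image task confounds discrimination with category preference. The loss is under 1 point at c = 0.25, about 2 points at c = 0.5 and about 7 points at c = 1 when d' = 1. It distorts session comparisons only if the lean differs between sessions. These sizes rest on the equal-variance model, balanced categories and assumed values of d' and c. With unequal category numbers, bias could move the score in either direction: with an assumed 60/40 face/house mix and d' = 1, it is 70.5% at c = −0.5 and 63.6% at c = 0.5.

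The primary yes/no analysis is not undermined. The change is still worth making, because it removes the dependence on category bias under the stated model and gives the trial a second, clearly defined discrimination measure.

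**What to change.** For each session, on real-image trials only, compute face/house d' = Z(P(F | face)) − Z(P(F | house)) and the matching bias c = −0.5 × [Z(P(F | face)) + Z(P(F | house))]. Prespecify a standard correction for cells at 0% or 100%. Report both beside percent correct, and state that scrambled trials are excluded from all three.

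Name face/house d' as a secondary outcome, analyse it with the same repeated-measures ANOVA, and state which FDR family it belongs to. Use it to inform the interpretation of a yes/no d' effect, not as a condition for claiming one: identifying a category and telling real from scrambled images are different discriminations and may legitimately diverge. Omit a split by recognised and unrecognised trials, or keep it descriptive. A 10-minute session with a mean pre-stimulus interval of 3 s allows fewer than 600/3 = 200 trials, so split cells could be sparse.

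The cost is a few lines of analysis on data already collected, one more secondary measure, and more cautious wording if the two measures disagree.
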